3.11.2.2. Analyses of Binary Outcomes

Analyses for proportion of participants with ≥ 1 -point decrease in fibrosis stage with no worsening of NASH on liver histology Week 52 from baseline will be conducted using the same statistical models as those used for evaluating the primary objective in Section 3.11.1.1. No worsening of NASH is defined as no increase in the NAS score.

Analyses for proportion of participants with ≥ 1 -point increase in fibrosis stage as well as proportion of participants that achieve a ≥ 2 -point decrease in NAS on liver histology, with ≥ 1 -point reduction in at least 2 NAS components (steatosis, hepatocellular ballooning, lobular inflammation) at Week 52 from baseline will be conducted using the same statistical models as those used for evaluating the primary objective in Section 3.11.1.1.

3.11.2.3. The Analysis Relative to the Treatment-Regimen Estimand

The analysis related to treatment-regimen estimand for all secondary outcomes may be conducted using the FAS. The same model described in Section 3.11.2.2 will be used for the analysis of binary outcomes. Missing values of the fibrosis score and components of NAS will be imputed according to Section 3.11.1.3.

For the mean body weight and mean absolute change in liver fat content by MRI-PDFF at Week 52, the analyses will be conducted utilizing ANCOVA described in Section 3.11.2.1. Imputation of missing data will be done with the jump-to-reference (placebo) imputation approach.

3.11.2.4. Additional Analyses of the Secondary Outcomes

Similar to primary outcomes, in the event of patients dropping out before Week 36, analyses may be repeated using the EXAS for exploratory purposes. The model and details of analysis is similar to what is described in Section 3.11.1.1.

3.11.3. Tertiary/Exploratory Efficacy Analyses

Unless otherwise specified, other secondary and exploratory efficacy analyses will be conducted using the EAS. Missing data will be handled through MMRM without utilizing multiple imputation technique (if applicable). Some biomarkers may be log transformed, if necessary.

3.11.3.1. Analyses of histological scores

Parts of the exploratory efficacy analyses include analyzing scores obtained from biopsy reads (e.g., components of NAS, fibrosis score, etc.). ANCOVA is utilized to perform the analysis in

such. Treatment, baseline T2DM status (Yes/No), and region (Japan, US including Mexico, and Europe including Israel) are the fixed effects in this model.

Table GPHR.3.2 describes appropriate analysis for tertiary/exploratory outcome with the objective of investigating the effect of tirzepatide 5 mg, 10 mg, or 15 mg SC QW versus placebo at different time points specified for each efficacy measure separately.

Table GPHR.3.2. Tertiary/Exploratory Efficacy

Efficacy Measure	Analysis Conducted	Additional Information
Mean change in the liver histology score for 
 • expanded ballooning score • expanded portal inflammation score • expanded fibrosis Stage 1 scores • Mallory-Denk body score, and • glycogenosis score 	ANCOVA in Section 3.11.2.1	Each of these items come from each pathologist's eCRF form and are not in the consensus form. As a result, the mean values from each pathologist will be used as the response variable.
Mean change in extracellular hepatic water content measured by iron-corrected T1 imaging (cT1, in ms) by MRI	MMRM model in Section 3.11.2.1	
Mean change in liver stiffness (in kPa) measured by TE	MMRM model in Section 3.11.2.1	
Mean change in ALT, AST, GGT, K-18, Pro-C3, ELF, FIB-4, adiponectin, leptin and ferritin	MMRM model in Section 3.11.2.1	ALT, AST, and GGT need to be log-transformed. Log-transformation may be applied to other biomarkers as appropriate.
Mean changes in fasting insulin and HOMA-IR	MMRM model in Section 3.11.2.1	Log-transformation may be applied as appropriate.
Mean change in waist circumference (centimeters)	MMRM model in Section 3.11.2.1	
Change in: 
 • PROMIS Fatigue Short Form 8a version 1.0 score • PROMIS Pain Interference Short Form 4a version 1.0 score • Chronic Liver Disease Questionnaire for Nonalcoholic Fatty Liver Disease (CLDQ-NAFLD) total and domain scores • Patient Global Impression of Severity (PGIS) 	ANCOVA model in Section 3.11.2.1	Psychometric analyses on PROs will be conducted by value, evidence, and outcomes (VEO) at Lilly
NASH resolution based on overall assessment of histology by pathologists	Logistic regression in Section 3.11.1.1	This directly comes from the pathologists consensus form in the CRF regarding determination if steatohepatitis is present.
Mean changes in NAS on liver histology	ANCOVA in Section 3.11.3.1	NAS is the sum of Steatosis, Lobular Inflammation, and Hepatocellular Ballooning scores directly from the pathologists consensus form in the CRF.

Efficacy Measure	Analysis Conducted	Additional Information
Mean change in the liver histology score for 
 • steatosis • hepatocellular ballooning, and • lobular inflammation 	ANCOVA in Section 3.11.3.1	Each of these items come directly from the pathologist's consensus form in the CRF.
Proportion of participants that achieve ≥ 1 -point improvement in the liver histology score for 
 • steatosis • hepatocellular ballooning, and • lobular inflammation 	Logistic regression in Section 3.11.1.1	Each of these items come directly from the pathologist's consensus form in the CRF.
Mean change in fibrosis stage on liver histology	ANCOVA in Section 3.11.3.1	This comes directly from the pathologist's consensus form in the CRF.
Proportion of participants with ≥ 2 -point decrease in fibrosis stage and no worsening of NASH on liver histology	Logistic regression in Section 3.11.1.1	No worsening of NASH is defined as no increase in the NAS score.
Proportion of participants classified with cirrhosis (F4) on liver histology	Logistic regression in Section 3.11.1.1	
Proportion of participants classified with absence of fibrosis on liver histology	Logistic regression in Section 3.11.1.1	
Mean percentage change in liver fat content by MRI-PDFF	MMRM model in Section 3.11.2.1	The analysis is done on relative changes in liver fat content at each measurement.
Proportion of participants that achieve a $\geq 30\%$ relative decrease in liver fat content by MRI-PDFF	Logistic regression in Section 3.11.1.1	The analysis should be done for Week 26 and Week 52 separately.
Mean percentage change in body weight	MMRM model in Section 3.11.2.1	
Proportion of participants that achieve $\geq 5\%$, $\geq 10\%$, $\geq 15\%$, or $\geq 20\%$ decrease in body weight	Longitudinal logistic regression model with the response variable of the percentage of participants achieving at least those percentages of body weight reduction at each scheduled postbaseline visit	The independent variables of the analysis model are treatment group, visit, treatment-by-visit interaction, and stratification factors (T2DM status and Region) as fixed effects and baseline body weight as a covariate.

Abbreviations: ALT = alanine aminotransferase; ANCOVA = analysis of covariance; AST = aspartate aminotransferase; CRF = case report form; eCRF = electronic CRF; ELF = Enhanced Liver Fibrosis panel; FIB-4 = Fibrosis-4 score; GGT = gamma-glutamyltransferase; HOMA-IR = Homeostatic Model Assessments for Insulin Resistance; K-18 = Keratin-18 M30 fragment; Lilly = Eli Lilly and Company; MMRM = mixed model for repeated measures; MRI = magnetic resonance imaging; NAS = NAFLD Activity Score; NASH = nonalcoholic steatohepatitis; PDFF = proton density fat fraction; PRO = patient-reported outcome; Pro-C3 = a fragment of the NH₂-terminal propeptide of type III procollagen; PROMIS = Patient Reported Outcome Measurement Information System; TE = transient elastography; T2DM = type 2 diabetes mellitus.

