3.3. Adjustments for Covariates

The study is stratified based on T2DM status (Yes or No) at randomization and the region (Japan, US including Mexico, and Europe including Israel).

For efficacy-related analyses of histological endpoints, region and T2DM status at randomization will be used as covariates. Unless otherwise specified, for efficacy analyses of continuous measurements including non-histological and laboratory biomarkers, corresponding baseline value will be used as an additional covariate to T2DM status and the region.

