3.11.2. Secondary Efficacy Analyses

3.11.2.1. Analyses of Continuous Outcomes

Analyses for change from baseline in body weight as well as mean absolute change in liver fat content by MRI-PDFF will be conducted using data in the EAS from baseline through the 52-week visit with the aid of an MMRM. REML will be used to obtain model parameter estimates and the Kenward-Roger option will be used to estimate denominator degrees of freedom. The response variable of the MMRM model will be the primary measure and model terms of interest will include treatment, visit, treatment-by-visit interaction, baseline T2DM status (Yes/No), and region (Japan, US including Mexico, and Europe including Israel) as fixed effects, and baseline values of the dependent variable as a covariate. An unstructured covariance structure will be used to model the within-patient errors. If this model fails to converge, the following covariance structures will be tested in the following order:

1. Heterogeneous Toeplitz
2. Heterogeneous First Order Autoregressive
3. Heterogeneous Compound Symmetry
4. Toeplitz
5. First Order Autoregressive, and
6. Compound Symmetry.

The first covariance structure that converges will be used. The resulting least squares mean estimate of mean change from baseline of each outcome will be summarized by visit and by study treatment.

If the outcome has only the baseline and end-of-treatment measurements, the analysis will be conducted utilizing ANCOVA. The response variable will be the continuous outcome and model terms will include treatment, baseline T2DM status (Yes/No), and region (Japan, US including Mexico, and Europe including Israel) as fixed effects, and baseline values of the outcome as a covariate.

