3.14. Safety Analyses

Unless specified otherwise, safety assessments will be based on the SS ([Table GPHR.3.1](#)). All events that occur between the date of first dose of study drug to the date of patient's safety follow-up visit or patient's end of study participation will be included, regardless of the adherence to study drug or availability of the end of treatment liver biopsy. For assessing the benefit and risk profile through 52 weeks, selected safety analyses will be conducted by utilizing safety data from first dose through the date of the 52-week visit.

The statistical assessment of homogeneity of the distribution of categorical safety responses among treatment arms will be conducted using Fisher's exact test, unless specified otherwise.

The mean change from baseline differences among treatments at all scheduled visits will be assessed via an MMRM using REML, unless specified otherwise. The model will include baseline T2DM status (Yes/No), the region (Japan, US including Mexico, and Europe including Israel), treatment group, visit and treatment-by-visit interaction as fixed effects, and baseline value of the safety parameter as a covariate. To model the covariance structure within patients, the unstructured covariance matrix will be used. If this model fails to converge, the covariance structures specified in Section [3.11.2.1](#) will be tested in order.

For selected safety parameters, time-to-first-event analysis via the Cox Proportional-Hazards model may be conducted. Patients without the event will be censored at the end of study participation. For patients experiencing the event, the "time-to-first-event" will be the time (in days) from first dose to first occurrence of the event.

Where necessary, the rate of events will be analyzed using a generalized linear mixed-effects model assuming the number of events follow a negative binomial distribution and with treatment as a fixed effect. The logarithm of days during the active treatment period will be adjusted as an offset to account for possible unequal treatment duration of follow-up between patients.

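### The exploratory ANCOVA for change in NAS, its components and fibrosis stage lists no baseline score, while other biopsy scores in the same table are adjusted for baseline

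*SAP*

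**What the plan says.** Section 3.11.3.1 of the SAP covers scores read from biopsies and assigns them an ANCOVA. Its full list of terms is: "Treatment, baseline T2DM status (Yes/No), and region (Japan, US including Mexico, and Europe including Israel) are the fixed effects in this model". In Table GPHR.3.2, the rows for mean change in NAS, for the three NAS components and for fibrosis stage are marked "ANCOVA in Section 3.11.3.1".

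The row for the expanded ballooning, expanded portal inflammation, expanded fibrosis Stage 1, Mallory-Denk body and glycogenosis scores is marked "ANCOVA in Section 3.11.2.1". That ANCOVA has the same three terms "and baseline values of the outcome as a covariate".

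The general rule in Section 3.3 has two sentences. On histology: "For efficacy-related analyses of histological endpoints, region and T2DM status at randomization will be used as covariates". On continuous measures: "Unless otherwise specified, for efficacy analyses of continuous measurements including non-histological and laboratory biomarkers, corresponding baseline value will be used as an additional covariate".

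**The concern.** Two sets of scores from the same biopsies are analysed with different covariate sets, and the SAP gives no reason. Two readings are open.

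- **A clause is missing.** Elsewhere the SAP lists fixed effects and then adds baseline separately. The body-weight responder row of Table GPHR.3.2 has "as fixed effects and baseline body weight as a covariate", and Section 3.14 has "as fixed effects, and baseline value of the safety parameter as a covariate". The label ANCOVA also suggests a continuous covariate, and none is named in 3.11.3.1.
- **The omission is deliberate.** The list matches the histology sentence of Section 3.3. In that case the expanded-score row departs from 3.3.

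On either reading some SAP text has to change. What is at stake is reproducibility and some precision. Programmers taking different readings would report different estimates, intervals and p-values for change in NAS and fibrosis stage. The listed model also leaves unused a baseline score that is already collected and summarized (SAP 3.8). No primary or secondary conclusion is involved: those histology endpoints are binary and use logistic regression.

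**Working it through.** **Model terms side by side**

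| Outcome (mean change) | Model | Baseline score listed? |
|---|---|---|
| NAS; steatosis, ballooning, lobular inflammation; fibrosis stage | 3.11.3.1 | No |
| Expanded ballooning, portal inflammation and fibrosis Stage 1; Mallory-Denk; glycogenosis | 3.11.2.1 ANCOVA | Yes |

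**Inputs.** The plan states no figure on this point. Protocol 1.1 expects about 157 evaluable participants, so 157/4 is about 39 per arm. The documents give no SD for these scores and no correlation between baseline and Week 52. I therefore assume a baseline SD s0, a Week 52 SD s1 and a correlation r from 0.2 to 0.5, on the 0 to 8 NAS scale. Entry requires NAS of at least 4 with at least 1 point per component, and fibrosis stage 2 or 3 (Protocol 5.1). This narrows the baseline spread, so s0 below s1 is more plausible than equal SDs.

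**Precision.** The variance per participant is:

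- change score, no baseline: s0² + s1² − 2·r·s0·s1
- with baseline: s1²(1 − r²)

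Example at s0 = 1.0, s1 = 1.6, r = 0.2: without baseline, 1 + 2.56 − 0.64 = 2.92; with baseline, 2.56 × 0.96 = 2.458. The ratio is 0.842, a saving of 15.8%. The interval width ratio is √0.842 = 0.917.

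| s0 / s1 | Saving at r = 0.2, 0.3, 0.4, 0.5 | Width ratio at r = 0.2 and 0.5 |
|---|---|---|
| 1.0 / 1.6 | 15.8%, 10.4%, 5.7%, 2.0% | 0.917 and 0.990 |
| 0.8 / 1.6 | 8.6%, 4.2%, 1.2%, 0.0% | 0.956 and 1.000 |
| 1.0 / 1.0 | 40%, 35%, 30%, 25% | 0.775 and 0.866 |

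**Cost of the extra covariate.** The listed model has 7 parameters: intercept, 3 for treatment, 1 for T2DM status and 2 for region. Adding baseline makes 8. With 157 participants the residual degrees of freedom go from 150 to 149, and 150/149 = 1.0067, or about 0.7% of variance.

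A simulation of both full models used 39 per arm, 25,000 trials and the three dose contrasts, with T2DM at 50% and regions at 10/60/30 as further assumptions. Net savings at r = 0.2 and 0.5, with simulation error of up to about a percentage point, were:

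- SDs 1.0/1.6: 14.4% and 1.0%
- SDs 0.8/1.6: 7.2% and −0.7%
- SDs 1.0/1.0: 38.7% and 23.5%

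Mean bias was about 0.001 points or less for both models.

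**Chance baseline imbalance.** If two arms differ by a gap g at baseline, the arm that starts higher appears to fall further by g(1 − r·s1/s0) in the unadjusted comparison. The standard error of the difference is √(2·Var(change)/39). Take g = 0.2 points.

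Example at 1.0/1.6, r = 0.2: 0.2 × (1 − 0.32) = 0.136 points. The standard error is √(2 × 2.92/39) = 0.387, so the shift is 0.35 SE.

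| s0 / s1 | Shift in points at r = 0.2, 0.3, 0.4, 0.5 | In standard errors |
|---|---|---|
| 1.0 / 1.6 | 0.136, 0.104, 0.072, 0.040 | 0.35, 0.28, 0.21, 0.13 |
| 0.8 / 1.6 | 0.120, 0.080, 0.040, 0.000 | 0.32, 0.23, 0.12, 0.00 |
| 1.0 / 1.0 | 0.160, 0.140, 0.120, 0.100 | 0.56, 0.52, 0.48, 0.44 |

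The direction is not fixed. Just outside the range, at 0.8/1.6 and r = 0.6, the shift is 0.2 × (1 − 1.2) = −0.040.

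**The case against.** The strongest reply is that the SAP is largely consistent as it stands. Section 3.3 has a sentence specific to histology that names region and T2DM status. Section 3.11.3.1 repeats those two terms with treatment, and the baseline default in 3.3 yields where a section specifies otherwise. The odd row would then be the expanded-score row. That reading is fair, but it still leaves a conflict to fix, and the default sentence can equally be read to cover continuous histology scores.

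The habit of adding baseline after the fixed effects is also not uniform. The pancreatic-enzyme model in Section 3.14.3.3.1 analyses a log ratio to baseline and lists no baseline covariate. This weakens the missing-clause reading but does not show that the omission in 3.11.3.1 was chosen.

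Table GPHR.3.2 does record one difference between the two sets. The expanded scores are averaged over the pathologists' individual forms, whereas NAS, its components and fibrosis stage come from the consensus form. The table uses this to define the response variable. It is not a reason for different covariates.

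Two limits on the size stand. The figures rest wholly on assumed SDs and correlations. They are also worked only for NAS, one of five affected measures. Baseline fibrosis stage is 2 or 3, and baseline ballooning, scored 0 to 2 with at least 1 required at entry, is 1 or 2. A two-valued score one point apart has an SD of about 0.5 at most, so the gain may be smallest there. Finally, SAP 3.2 already allows additional analyses, so a baseline-adjusted version could be run anyway. That does not settle which model is the planned one.

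**Conclusion.** The point holds, as a minor one. The textual mismatch is certain: the listed model for change in NAS, its components and fibrosis stage has no baseline score, the expanded scores in the same table do get one, and Section 3.3 does not decide between them. The benefit of adding baseline is less certain. For NAS, under the assumed range, intervals narrow by 1% to 8% at SDs 1.0/1.6, by 0% to 4% at 0.8/1.6, and by 13% to 23% at equal SDs, the less likely case. The gain is small to moderate and may be nil. The unadjusted analysis is not biased.

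**What to change.** Add the corresponding baseline score as a covariate to the model sentence in SAP 3.11.3.1, or point the NAS, component and fibrosis-stage rows of Table GPHR.3.2 to the ANCOVA of 3.11.2.1. In either case, reword the histology sentence of Section 3.3 so that it agrees for mean-change scores. If the omission is deliberate, say so, give the reason, and explain why the expanded scores are treated differently. The logistic models need no change.

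The cost is SAP wording and one degree of freedom. No new data are needed.

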### **Prior/Concomitant Therapy**

- 51. Have used insulin for treatment of diabetes within the prior year. However, short-term use of insulin for acute conditions is allowed (≤14 days) in certain situations, such as during a hospitalization or perioperatively (See Section 6.5.1.2)
- 52. Current or previous (within 3 months of screening) use of GLP-1 receptor agonists or any history of allergies to these medications.
- 53. Use of drugs associated with hepatic steatosis (e.g., amiodarone, methotrexate, tamoxifen) for more than 2 weeks in the 3 months prior to screening. If the use of such drugs is anticipated to be medically necessary within the next year, the patient should also be excluded.
- 54. Current use of medication associated with weight gain, except when on stable dose for at least 3 months prior to screening and remaining on stable dose during the study
- 55. Receiving or having received (within 3 months of screening) chronic (>2 weeks) systemic glucocorticoid therapy (excluding topical, intra-ocular, intranasal, intra-articular, or inhaled preparations) or have evidence of a significant active autoimmune disease (such as systemic lupus erythematosus or rheumatoid arthritis) that has required (within the last month) or is likely to require (in the opinion of the investigator) concurrent treatment with systemic glucocorticoids (excluding topical, intra-ocular, intranasal, intra-articular or inhaled preparations) in the next 12 months
- 56. Use of medications or alternative remedies (within 3 months prior to screening; prescribed or over-the-counter) intended to promote weight loss. These include, but are not limited to: Saxenda [liraglutide 3.0 mg], Alli®/Xenical® [orlistat], Meridia® [sibutramine], Acutrim® [phenylpropanolamine], Sanorex® [mazindol], Apidex® [phentermine], BELVIQ® [lorcaserin], QsymiaTM [phentermine/topiramate combination], Contrave® [naltrexone/bupropion]. (See also Inclusion criteria #9)
- 57. Unwillingness to discontinue over-the-counter (herbal) medication that, in the opinion of the investigator, can interfere with the study
- 58. Active and chronic use of anticoagulants (other than aspirin or nonsteroidal anti-inflammatory drugs [NSAIDs]) that, in the opinion of the investigator, increases the risk of severe bleeding during the liver biopsy.

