### 6.5.1. Hyperglycemia Rescue

Although the use of rescue medications is allowable during the study, the use of rescue medications should be delayed, if possible, for at least 1 month after initiation of study drug. The date and time of rescue medication administration as well as the name and dosage regimen of the rescue medication must be recorded.

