### **6.5.1.2.** Hyperglycemia Rescue Medication

Participants with T2DM who develop persistent severe hyperglycemia during the treatment period may be candidates for glucose-lowering rescue therapy and should be considered for addition of, or dose increases of, glucose-lowering medications.

The study site will supply rescue medication that will be obtained locally. Initiation or dose increase of the following may be used as rescue therapy:

- Metformin
  - Do not initiate or increase the dose of metformin when the eGFR
     <45 mL/min/1.73 m² (or lower than country-specific threshold for using the prescribed dose of metformin per local label)

- Sulfonylureas
- Long-acting basal insulin, when
  - o Participant has persistent severe hyperglycemia, and
  - o Participant is at maximal tolerated doses of metformin and/or sulfonylurea (or has an intolerance or contraindication to these medications)

Dose increases of the following are NOT allowed during the study:

- SGLT-2 inhibitors
- TZDs

Initiation of the following is NOT allowed during the study:

- GLP-1 receptor agonists (See Section 5.2)
- DPP-4 inhibitors (See Section 5.2).
- SGLT-2 inhibitors
- TZDs

While avoiding the classes of glucose-lowering medications not allowed by the protocol, investigators should follow national standards of care for diabetes management in respective

participating countries or the American Diabetes Association/European Association for the Study of Diabetes guidance (Inzucchi et al. 2015).

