### 8.1.3.5. Homeostatic Model Assessment for Insulin Resistance (HOMA-IR)

The effect of tirzepatide on insulin sensitivity will be evaluated based on the change from baseline in HOMA-IR.

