- Population: participants who meet the inclusion criteria. Further details can be found in Section 5 of Protocol GPHR.
- Endpoint: NASH resolution without worsening of fibrosis at 52 weeks.
- Treatment condition: the randomized treatment.
- The ICE “permanent discontinuation of study drug” is handled by the hypothetical strategy and the potential outcome of interest is the response in the efficacy measurement if participants had adhered to the randomized treatment. There are no other defined ICES.
- Population-level summary: proportion of patients meet NASH resolution without worsening of fibrosis at Week 52.

Treatment effect of interest is thus defined as the difference in proportion of NASH resolution without worsening of fibrosis at Week 52 between QW LY3298176 (tirzepatide) and placebo. Rationale for “efficacy estimand”: This Phase 2 study aims to study the efficacy of LY3298176 (tirzepatide) under the ideal condition that all participants adhere to the randomized treatment. Data collected after the ICE will be set to missing.

Estimand(s) for Secondary Objectives

The same estimand for the primary objective will be used for the secondary efficacy endpoints for the secondary objectives.

Treatment-regimen estimand

The second estimand, the “treatment-regimen” estimand, represents the efficacy irrespective of adherence to investigational product and availability of the postbaseline biopsy. There are no ICE.

Unless specified otherwise, safety analyses will be conducted using the SS.

The end of study participation for a patient will be the earliest of date of death, date of withdrawal from further participation in the study, or date of the safety follow-up visit (Visit 801). For patients considered to be lost to follow-up, end of study participation will be the date of lost to follow-up reported by the investigator. Patient data included in the database after the last date of study participation (date of death, date of early termination or date of safety follow-up) will be excluded from statistical analyses. A listing of such data may be provided.

Summary statistics for categorical measures (including categorized continuous measures) will include sample size, frequency, and percentages. Summary statistics for continuous measures will include sample size, mean, SD, median, minimum, and maximum. The summary statistics

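### Fasting insulin and HOMA-IR values taken on rescue basal insulin stay in the exploratory analysis, although they no longer measure the participant's own insulin or insulin sensitivity

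*SAP*

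**What the plan says.** Protocol 8.1.3.5 makes HOMA-IR the test of mechanism: "The effect of tirzepatide on insulin sensitivity will be evaluated based on the change from baseline in HOMA-IR". Fasting insulin and HOMA-IR are tertiary/exploratory endpoints. SAP Table GPHR.3.2 lists them as "Mean changes in fasting insulin and HOMA-IR", analysed with the MMRM of SAP 3.11.2.1. The only added note is that a log transformation may be applied.

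On the data used, SAP 3.11.3 says "other secondary and exploratory efficacy analyses will be conducted using the EAS". SAP Table GPHR.3.1 defines the EAS as treatment-period data from randomized participants, cut off only at permanent study drug discontinuation. SAP 3.2 names that discontinuation as the intercurrent event of the efficacy estimand and adds "There are no other defined ICES". SAP 3.11 applies this estimand to the exploratory endpoints as well.

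On insulin, exclusion 51 removes those who "Have used insulin for treatment of diabetes within the prior year", with an exception for short-term acute use. After randomization, Protocol 6.5.1 begins "Although the use of rescue medications is allowable during the study", and 6.5.1.2 lists among the options "Long-acting basal insulin, when" two conditions hold. One is persistent severe hyperglycemia. The other is "Participant is at maximal tolerated doses of metformin and/or sulfonylurea (or has an intolerance or contraindication to these medications").

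**The concern.** HOMA-IR can be read as insulin resistance only if the insulin in it is what the participant secretes. At baseline that is nearly always so, because of exclusion 51. Once basal insulin starts, the measured value depends on the injected dose, on how far the assay detects the product, and on how far the participant's own secretion is suppressed. A change from baseline then compares two different quantities.

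At stake is the only insulin-sensitivity comparison in the plan. Both measures listed under that objective contain measured insulin, so neither can check the other. The primary and secondary endpoints are not touched.

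**Working it through.** The plan states no figure on this point, so the check is mainly of text.

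**Do on-insulin values reach the model?**

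1. Basal insulin is permitted rescue (Protocol 6.5.1.2).
2. Rescue is not among the reasons for stopping study drug in Protocol 7.1, so a rescued participant normally stays on treatment. The step there of calling the sponsor when an exclusion criterion develops is case by case and is not a data rule.
3. The SAP's EAS cuts data only at permanent discontinuation (Table GPHR.3.1). The protocol's narrower EAS (9.3) also cuts only at discontinuation. The FAS, which Protocol 9.4.3.3 allows as an alternative for endpoints not needing a biopsy, keeps data regardless of adherence.
4. Insulin is sampled at Weeks 0, 12, 20, 26, 40 and 52 in the treatment period (Protocol 1.3), so affected values can reach the Week 52 contrast.
5. Rescue use is only summarised (Protocol 9.4.2.3, SAP 3.10). No section removes or flags the laboratory values.

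The answer is yes.

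**How large could the effect be?** The documents give no insulin rescue rate, no SD and no assay details, so the inputs below are assumptions, apart from the roughly 40 completers per arm (Protocol 9.2).

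Let k participants in one arm of 40 be on insulin, with measured fasting insulin multiplied by f.

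- Log scale: change in that arm's geometric mean = exp((k/40) × ln f) − 1
- Raw scale, assuming average starting values: change in the mean = k(f − 1)/40

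| k | Log scale, f = 2 | Log scale, f = 4 | Raw scale, f = 2 | Raw scale, f = 4 |
|---|---|---|---|---|
| 1 | 1.7% | 3.5% | 2.5% | 7.5% |
| 2 | 3.5% | 7.2% | 5.0% | 15.0% |
| 4 | 7.2% | 14.9% | 10.0% | 30.0% |

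If the assay does not detect the product and own secretion is suppressed, f is below 1. With f = 1/2 or 1/4 and k = 1, the log-scale change is −1.7% or −3.4%. With equal k and f in both arms, the bias in the contrast is zero.

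**Is k plausible?** T2DM participants are 40% to 65% of the study (Protocol 4.1), which is 0.40 × 40 = 16 to 0.65 × 40 = 26 per arm. So k = 4 would mean 4/26 = 15% to 4/16 = 25% of an arm's T2DM participants on insulin. Nothing in the documents supports a share that high.

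**Against sampling error.** Assume a log-scale SD of 0.4 to 0.7. The standard error of a two-arm difference is SD × √(2/40) = 0.09 to 0.16. One affected participant shifts the log mean by ln 2/40 = 0.017 to ln 4/40 = 0.035, about 0.1 to 0.4 standard errors.

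**HOMA-IR.** The protocol does not print the formula. In its usual form HOMA-IR is proportional to fasting insulin times fasting glucose. If rescue multiplies glucose by h < 1, the log shift becomes (k/40)(ln f + ln h). For f > 1 this is smaller than for insulin alone, as long as the fall in glucose does not outweigh the rise in measured insulin.

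**The case against.** The strongest case against the point is that it is minor and unsigned. Insulin rescue is tightly restricted, the endpoints are exploratory in a study without multiplicity control, rescue imbalance will be visible in the planned summaries, and SAP 3.2 allows further analyses without amendment. This stands as a limit on importance. It does not make the retained values valid, and a rule chosen after unblinding is weaker than one written now.

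A reader might infer that placebo insulin and HOMA-IR will be inflated and the drug effect overstated. More rescue on placebo is a reasonable inference, since Protocol 8.3.7.6 notes that tirzepatide lowers glucose. But no rescue rates by arm are given, and the sign also depends on an assay and an insulin product that the documents do not name. The stronger reading is not supported.

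A reader might also infer that C-peptide, collected at the same visits, could replace HOMA-IR for participants on insulin. It cannot. It reflects own secretion, which injected insulin suppresses, and it does not measure insulin sensitivity.

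Two further objections concern the remedy. Metformin and sulfonylurea rescue can also change insulin or glucose. In those cases the assay still measures the participant's own insulin, so the issue is which effect to estimate, not whether the measurement is valid. Setting values to missing also gives these two endpoints a rule that the others lack. That is justified because a body weight or liver fat value after rescue is still a valid measurement of what it claims to measure.

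**Conclusion.** The point holds as a gap in the data rules for two exploratory endpoints. As written, the plan analyses fasting insulin and HOMA-IR values taken on injected basal insulin as if they were the participant's own.

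The bias cannot be signed or sized from the documents. On the assumed inputs it is a few percent of an arm's geometric mean for one or two affected participants, larger if the analysis stays on the raw scale, and zero if nobody receives insulin. It is probably small. The conclusion that the values are unsuitable for this purpose does not depend on the sign or on which arm has more rescue.

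**What to change.** In SAP Table GPHR.3.2, for fasting insulin and HOMA-IR only:

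- Set to missing the values taken while on exogenous insulin: from the start of ongoing rescue insulin, or only during use when it is short-term.
- Commit to the log scale.
- Report the number on insulin by arm and visit.
- Show the analysis of all values as a sensitivity analysis.
- Optionally add the same MMRM for fasting C-peptide, described as supportive evidence on endogenous secretion and not as a replacement for HOMA-IR.

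No new data are needed. Protocol 6.5.1 already requires the date, name and dosage of rescue medication, and C-peptide is drawn at the same visits but has no analysis in the table. The cost is SAP wording, one flag and one or two extra models. The downside is that a few post-rescue values are lost, probably from poorly controlled participants, and the MMRM then relies on missing at random for them. The sensitivity analysis and the counts by arm let a reader judge how much that matters.

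Separately, Protocol Appendix 9 lists long-term insulin treatment as prohibited under exclusion 51, while 6.5.1.2 permits long-acting basal insulin as rescue. These passages must be reconciled.
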